Information about civil registration number, phone number, address, diagnosis of T1D and historic levels of urine albumin on outpatients at Steno Diabetes Center Copenhagen is provided by the treatment-responsible doctor and passed on to the study investigator. This information is used for identifying possible participants and recruitment. First contact will be a letter containing the written participant information and the brochure: "Your rights as a participant in biomedical research". In the letter, possible participants will be invited to the information meeting at Steno Diabetes Center Copenhagen. The letter contains telephone number and email for the project-responsible doctor. Non-responders will be followed up by a telephone contact approximately two weeks later. All who wish to participate in the study are invited for an information visit.

Healthy controls will be recruited by advertisement in the local newspapers. In the advertisement, there will be phone number and email of the investigators for contact.

Endpoints

Primary end-point

- Renal oxygenation (T_2^*)

Exploratory end-points

[figure not shown]
- Renal cortical and medullary perfusion
- Renal artery flow
- Renal oxygen consumption
- Peripheral capillary oxygen saturation (SpO_2)
- Arterial blood gasses
 - Arterial blood oxygen partial pressure (PaO_2)

- Arterial blood oxygen saturation (SaO₂)
- PBMC mitochondrial function
- Circulating inflammatory markers
- Baroreflex sensitivity

Study design

Randomized, double blinded, placebo-controlled, cross-over intervention study in patients with type 1 diabetes. Baseline results will be compared to healthy controls.

Figure 1

Flowchart of study design. Healthy controls (CON) will only come for baseline measurements on V1 and V2, except blood gas analysis, which will only be done in randomized patients.

Patients with type 1 diabetes (T1D) will be randomized to SGLT2i or placebo for Visits 1+2 and crossed over for Visits 3+4.

Comparative treatment regimes

Patients in the active arm will be treated with dapagliflozin 50 mg once on site for V2 and once at home on the evening before V3.

Randomization and blinding

Patients will be randomly assigned in a 1:1 ratio to one of the following groups:

- Dapagliflozin for V2 and V3 and placebo for V4 and V5
- Placebo for V2 and V3 and dapagliflozin for V4 and V5

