Scanning will be performed on a 3-T Philips Achieva scanner using the scanners body transmit and a four-element SENSE cardiac receive coil. Subjects will be scanned using MRI sequences to map ASL perfusion and BOLD T_2^* in the kidneys and to measure flood flow in the renal artery. Renal oxygen consumption will be measured using Q-flow combined with measurement of BOLD in the renal artery and vein. All measurements will be performed twice.

Mitochondrial function

Mitochondrial function will be quantified by using the Seahorse 96XF Analyzer (Agilent Technologies, Santa Clara, CA, USA) that can measure oxygen consumption rate and extracellular flux in real time in a 96-well plate in intact peripheral blood monocytes (PBMCs). Extracellular flux is changes in oxygen and proton concentrations in the media surrounding the PBMCs. From this, the relative state of aerobic and glycolytic metabolism can be

determined. Thus, the Seahorse assays can quantify enzyme defects, including oxidative phosphorylation, glycolytic pathway abnormalities and fatty acid oxidation pathway abnormalities (21).

Circulating inflammatory markers

Inflammatory markers will be measured on venous blood with a validated assay including 92 inflammation-related human protein biomarkers simultaneously (Olink, Uppsala, Sweden) (22).

Baroreflex sensitivity

Baroreflex sensitivity is defined as the change in heart-rate in relation to change in blood pressure. It is considered a sensitive measurement of cardiovascular autonomic function (19). Baroreflex sensitivity will be determined from spontaneous fluctuations in the RR interval and systolic blood pressure. We will use a method earlier described in detail (23, 24).

Blood samples

From healthy controls, a total of 21 ml of blood will be taken at V1. From randomized patients, a total of 21 ml of blood will be taken at V1, 3 ml blood at V2, 11 ml blood at V3, 3 ml blood at V4 and 11 ml blood at V5. The material will only be used for analysis in the Astronaut study and will be destroyed at the end of the study.

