Mitochondrial function		x		x		x
Inflammatory markers		x		x		x
Baroreflex sensitivity		x		x		x
Kidney MRI			x		x	
Pulse oximetry			x		x	
Blood gas analysis			x		x	
Safety						
Adverse events			x	x	x	x
Study medication						
Drug accountability				x		x

Study timetable for randomized patients. SDCC = Steno Diabetes Center Copenhagen, RHG = Rigshospitalet Glostrup.

Assessment of efficacy

In order to assess the acute physiological response of inhibiting SGLT2 in the proximal tubule, kidney MRI parameters, pulse oximetry and blood gas analysis are obtained before intervention (baseline), three hours after intervention and six hours after intervention. In order to assess the subacute, systemic physiological response, PBMC mitochondrial function, inflammatory markers and baroreflex sensitivity are obtained before intervention (baseline) and 12 hours after intervention. Baseline levels will be compared to those of healthy controls.

Response to dapagliflozin in outcomes in randomized patients will be compared to response to placebo.

Assessment of safety

Definition of SAE, SAR and SUSAR

Serious Adverse Event (SAE):

A Serious Adverse event is an experience that treatment results in any of the following:

- Results in death
- Is life threatening (note: the term life-threatening refers to an event in which the patient was at risk of death at the time of the event; it does not refer to an event which hypothetically might have caused death if it was more severe)
- Requires inpatient hospitalization or results in prolongation of existing hospitalization
- Results in persistent or significant disability/incapacity
- Is a congenital anomaly/birth defect, or
- Is an important medical event that may not result in death, be life-threatening, or require hospitalisation may be considered a serious adverse event when, based upon appropriate medical judgement, they may jeopardise the patient or subject and may require medical or surgical intervention to prevent one of the outcomes listed in this definition.
- Suspicion of transmission of infectious agents must always be considered an SAE.

Serious Adverse Reaction (SAR):

A SAE for which a causal relationship to the study medication is at least possible i.e. a causal relationship is conceivable and cannot be dismissed.

Suspected Unexpected Serious Adverse Reaction (SUSAR):

A SAE which is unexpected and regarded as possibly or probably related to the study medication by the Investigator.

Reporting of SAE SAR and SUSAR

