All events meeting the definition of an AE must be collected and reported. This includes events from the first study-related activity after the subject has signed the informed consent until the end of the study. When reporting Adverse Events the following parameters must be recorded: study name, patient identification (subject number, initials, sex, age), event (preferably a diagnosis), IMP, reporter identification (name or initials), causality, outcome. Timelines for reporting of AE's is described in study timetable.

Assessment of adverse event

The following three definitions are used when assessing the severity of an AE: Mild (no or transient symptoms, no interference with the subject's daily activities), Moderate (marked symptoms, moderate interference with the subject's daily activities) and Severe (considerable interference with the subject's daily activities; unacceptable).

The following terms are used when assessing the causality between an AE and the IMP: Probable (good reason and sufficient documentation to assume a causal relationship), Possible (a causal relationship is conceivable and cannot be dismissed) and Unlikely (the event is most likely to ethology other than the IMP (Forxiga®).

Reporting at the end of the study

A final report on the AEs and SAEs is sent to the Danish Medicines Agency, the Regional Scientific Ethics Committee and to AstraZeneca within 12 months after the last patient has completed the project.

Statistical considerations

Sample size

The primary goal is to test the hypothesis that SGLT2 inhibition will improve renal oxygenation with a lowering of medullary T_2^* , as a marker of increased oxygenation. A power calculation was performed, based on data available from the study by Haddock. et al. (15). The mean \pm SD resting medullary T_2^* was 23 ± 4 . Assuming that SGLT2 inhibition will improve oxygenation 20%, the sample size required to demonstrate a significant effect with a power of 80% and a type 1 error of 5%, is 13 subjects per group. To account for technical difficulties, we included 15 in each group. Power calculation was performed using the power statement implemented in the SAS enterprise software 7.1 (SAS Institute, Cary, NC, USA).

Analysis

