All characteristics will be presented as means with standard deviation (SD) or if skewed distributions, as medians with interquartile range (IQR). For baseline characteristics, chi-squared test and Fischer's exact test will be used when appropriate. For testing group differences, unpaired student's t-test will be used. For testing the effect of the intervention, linear regressions analyses will be performed adjusting for baseline values of outcome variables. To fulfil the requirement of a normal distribution of the model residuals, determinants will be log-transformed where appropriate. Statistical significance is inferred as a two-tailed P-value < 0.05 . All analyses will be performed in SAS enterprise 7.1.

Data management

Source data identification and source data verification

All clinical study information in this study will be recorded, handled, and stored in a way that allows it accurate reporting, interpretation and verification.

Sponsor/investigator will provide direct access to source data/documents for study related monitoring, audit, IEC/IRB review, and regulatory inspection. Sponsor has made an agreement with the GCP-unit at the University of Copenhagen, Denmark, who will be monitoring the study in accordance with the ICH guidelines for GCP.

Subject data protection

There will be a transfer of information from the doctor responsible for the person in the clinic to the doctor responsible for the research of relevance to study participation and safety in the personal record. All information on study subjects is protected according to law on processing of personal data and the law of health. None of the study related blood samples or data will be stored or analyzed in countries outside the EU.

Data handling

Before initiating the study acceptance from the Danish Data Protection Agency will be obtained. A separate case report form (CRF) will be prepared for each study participant. All health-related matters and sensitive personal data will be handled in accordance with the Danish "act on Processing of Personal Data".

All health-related matters and sensitive personal data (CRF, blood test result etc.) will be depersonalized. All participants will be given a study number referring to their personal information, which will be stored securely and separately. Adequate blinding of all personal data during data processing and publication will be ensured.

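### No multiplicity control is stated for the exploratory 92-protein panel; under the plan's general P < 0.05 rule, up to about 4.6 false positives per comparison are expected if no protein truly differs

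*Combined protocol and SAP*

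**What the plan says.** Methods, under Circulating inflammatory markers, describes one assay covering "92 inflammation-related human protein biomarkers simultaneously". Table 2 schedules it at V1, V3 and V5. The Endpoints section lists "Circulating inflammatory markers" among the exploratory end-points. No individual protein is singled out, no summary score is defined, and the Hypothesis section makes no prediction about inflammation.

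Assessment of efficacy sets two comparisons for the outcomes, including these markers: "Baseline levels will be compared to those of healthy controls", and "Response to dapagliflozin in outcomes in randomized patients will be compared to response to placebo".

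Statistical considerations, Analysis, supplies the tests. For the first comparison: "For testing group differences, unpaired student's t-test will be used". For the second, "linear regressions analyses will be performed adjusting for baseline values of outcome variables". It then gives a single threshold for everything: "Statistical significance is inferred as a two-tailed P-value < 0.05". Nothing in the document mentions multiplicity, a false discovery rate, or a descriptive-only reading of exploratory results.

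**The concern.** A panel of 92 markers with no named protein of interest works as a screen. If a screen is read with the same per-test threshold as a single end-point, some proteins can be expected to cross it by chance. The exploratory label does not settle this, because the Analysis section does not confine its significance rule to the primary end-point.

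What is at stake is the credibility of any published list of significant proteins, both for the disease comparison and for the drug comparison. The Publication plan commits to reporting positive, negative and inconclusive results, so protein findings are likely to be published. As the plan stands, a reader of that list would not know what share of it to expect by chance.

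**Working it through.** **The plan's own figure.** The plan gives no error rate or expected count for the panel. Its only design calculation is for the primary end-point: "resting medullary T_2^* was 23 ± 4", a 20% change (0.20 × 23 = 4.6 in T2* units, which matches the count below only by coincidence), 80% power and 5% type 1 error. An exact two-sample t-test calculation gives power 0.768 at 12 per group and 0.803 at 13, so the stated 13 per group is reproduced. That calculation does not cover the proteins.

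**Inputs for the panel.**
- Number of proteins: 92 (Methods).
- Two-sided threshold: 0.05 (Analysis).
- Comparisons: two (Assessment of efficacy).
- Sample: 15 patients and 15 controls at baseline; 15 patients in both cross-over periods.
- Assumed, because the documents do not give them: the share of proteins that truly differ, the effective number of independent tests, and the within-patient correlation.

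**Step 1: expected false positives.** Expected count = (number of proteins with no true difference) × (actual size of each test). Independence is not needed.
- No true differences, 5% size: 92 × 0.05 = 4.6 per comparison, or 184 × 0.05 = 9.2 over both.
- 10% truly differ: 82.8 × 0.05 = 4.1.
- 25% truly differ: 69 × 0.05 = 3.5.
- 50% truly differ: 46 × 0.05 = 2.3.

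**Step 2: chance of at least one, with no true differences.** With m independent tests this is 1 − 0.95^m.
- m = 92: 0.991.
- Correlated proteins, represented by an assumed 10, 30 or 50 effective tests: 0.40, 0.79 or 0.92. The expected count in Step 1 stays at 4.6.

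**Step 3: size of the drug comparison as written.** The regression adjusts for baseline but names no patient term. Ignoring the pairing in a cross-over makes the test conservative. A simulation (15 patients, two periods, one shared V1 baseline, no true effect, 20,000 runs) gave:

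| Assumed within-patient correlation | Actual test size | Expected false positives of 92 |
|---|---|---|
| 0 | 0.050 | 4.6 |
| 0.3 | 0.029 | 2.7 |
| 0.5 | 0.023 | 2.1 |
| 0.7 | 0.015 | 1.3 |
| 0.9 | 0.009 | 0.8 |

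A model that handles the pairing properly would bring the size back to about 5% and the count to about 4.6. The patient-control comparison uses an unpaired t-test on different people, so this step does not apply to it.

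**Step 4: what adjustment costs.** Bonferroni is stricter than Benjamini-Hochberg, so it bounds the cost. Its per-protein threshold is 0.05/92 = 0.00054. The effect detectable with 80% power at n = 15 rises from 1.06 to 1.76 SD (unpaired), and from 0.78 to 1.41 SD of the within-patient difference (paired).

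**The case against.** The strongest reply is that the panel is exploratory. It is absent from the Hypothesis section and from the Summary's end-point list, and no sample size rests on it. Unadjusted P-values are commonly accepted for such end-points when they are read as exploratory. This stands as a limit on the weight of the point. It does not close the gap, because the plan never says that exploratory P-values are descriptive and applies its inference rule to all of them.

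A second reply is that the plan does not say each protein will be tested separately, nor that P-values will be unadjusted. That is correct. Both are the plain reading of a single general rule combined with silence about the panel, so this is a missing specification and not a declared method.

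Readers might also infer stronger conclusions that the documents do not support:
- *About five false findings will arise in every comparison.* The figure of 4.6 needs no true differences and exact 5% size. Patients with albuminuric type 1 diabetes may truly differ from healthy people on some proteins, and the drug regression may be conservative as written.
- *False findings are almost certain.* The 99.1% depends on independence. Proteins chosen for one biological theme are plausibly correlated.
- *True signals cannot be told from chance ones.* Nothing in the plan shows this. A very small P-value remains distinguishable from a borderline one, and false-discovery-rate control relies on that.

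Finally, Benjamini-Hochberg is not the only remedy. A statement that the protein P-values are purely descriptive would also close the gap, but would give the reader no error-controlled list.

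**Conclusion.** The omission is real and its weight is modest. A single P < 0.05 rule covers a 92-protein screen in two comparisons, with no stated error control. The 4.6 per comparison is an upper figure, reached only under the two conditions above, and it rests on the inference that every protein is tested under the general rule. Across the assumptions examined, the expected count runs from 4.6 down to 2.3 for patients against controls, and from 4.6 down to 0.8 for the drug comparison with no true effect. The chance of any false positive is material throughout the assumed range of 10 to 50 effective tests when no protein differs.

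The type I error of the primary T2* end-point is not touched. This is a cheap improvement to the analysis of an exploratory end-point and does not threaten the trial's main conclusion.

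**What to change.** Add to Statistical considerations, Analysis:

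*For the 92-protein inflammation panel, P-values will be adjusted by the Benjamini-Hochberg procedure at a 5% false discovery rate, separately within each comparison (patients versus controls; dapagliflozin versus placebo). Only proteins with q < 0.05 will be called significant. All estimates will be tabulated with their unadjusted P-values and labelled exploratory.*

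This takes a few sentences in the plan and about one line of code. Design, visits and sample size do not change. The downside is that fewer proteins will be called significant with 15 patients. The loss of sensitivity is no worse than the Bonferroni bound in Step 4, and the full table keeps the unadjusted results available for generating hypotheses.

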We hypothesize that SGLT2 inhibition acutely reduces the kidneys demand for oxygen by reducing renal metabolism due to blocked sodium-glucose transportation, and hyperfiltration. We hypothesize that the following changes can be demonstrated after institution of SGLT2 inhibition:

- 1) Lowering of renal artery flow (PC-MRI)
- 2) Lowering of renal cortical perfusion and the ratio of cortical/medullary perfusion (ASL-MRI)
- 3) Better medullary oxygenation: Lowering of the renal medulla T_2^* (BOLD-MRI)
- 4) Decrease of renal oxygen consumption (Q-flow combined with measurement of BOLD in renal artery and vein)

We further hypothesize that autonomic function will improve, and that peripheral blood oxygenation and mitochondrial function will both increase after institution of SGLT2 inhibition.

Study population

Fifteen healthy controls recruited through an advertisement in the local newspapers and 15 persons with type 1 diabetes recruited from Steno Diabetes Center Copenhagen according to the study in-and exclusion criteria.

Inclusion criteria healthy controls:

- Written informed consent must be provided before participation
- Male or female patients > 18 years of age
- Capable of lying in a MR-scanner for two hours

Inclusion criteria persons with type 1 diabetes:

- Written informed consent must be provided before participation
- Male or female patients >18 years of age with a diagnosis of type 1 diabetes (WHO criteria)
- Urinary albumin creatinine ratio (UACR) ≥ 30 mg/g in 2 out of 3 consecutive samples (albuminuria) prior to randomization assessed from electronic laboratory database.
- Capable of lying in a MR-scanner for two hours

Exclusion criteria for all:

- Non-diabetic kidney disease as indicated by medical history and/or laboratory findings
- Renal failure (eGFR<15 ml/min/1.73m²), dialysis or kidney transplantation
- Treatment with beta-blocking medication
- Uncontrolled arrhythmia, 2. or 3. degree AV-block or sick sinus syndrome - assessed from a standard 12-lead electrocardiogram
- Pregnancy or breastfeeding (urine HCG is performed on all fertile women)
- Systolic blood pressure < 90 or > 200 mmHg
- Patients who, in the judgement of the investigator, is incapable of participating
- Exclusion criteria for MRI
 - Claustrophobia
 - Known heart disease

- Known lung disease
- Have had surgery the past six weeks
- Have foreign bodies of metal in the body (e.g. pacemaker, metal plates, metal screws)

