Information about the study background, design and aspects of the study will be given by the investigator. After consideration, the participants interested in participating in the study are asked to sign an informed consent form. After signed informed consent, patients will be randomized. See section "Participant information/informed consent" for details on informed consent.

Visit 1 (day 7±6) at Steno Diabetes Center Copenhagen

The study participant will come fasting from the morning and abstinent from medication, alcohol and tobacco use except long-acting insulin, 24 hours before the visit. The study participant is not allowed to do strenuous exercise 24 hours prior to the examination. Visit 1 will take approximately two hours. The following questions, measures and samples are obtained:

- Demographic information, medication and medical history are obtained from electronic medical journal and by interview with the study participant
- Weight and height for calculation of body mass index (BMI)
- Office blood pressure and heart rate
- Routine biochemistry
- Test battery A (baseline)
 - Analysis of mitochondrial function of peripheral blood monocytes
 - Sample kept in research biobank for analysis of inflammatory markers
 - Baroreflex sensitivity assessed by continuous ECG and blood pressure

Visit 2 (day 14±6) at Rigshospitalet Glostrup

The study participant will come fasting from the morning and abstinent from medication, alcohol and tobacco use except long-acting insulin, 24 hours before the visit. The study

participant is not allowed to do strenuous exercise 24 hours prior to the examination. Visit 2 will take approximately eight hours. The following measures will be obtained:

- Test battery B (baseline)
 - MRI session with two measurements of: Renal perfusion, renal artery flow, renal oxygen consumption and T_2^* respectively
 - Peripheral blood oxygen saturation by pulse oximetry
 - Blood gas analysis

A standardized morning meal will be given together with the intervention: Institution of 50 mg SGLT2i/placebo. Exactly three hours after intervention, test battery B will be repeated:

- Test battery B (+3 hours)
 - MRI session with two measurements of: Renal perfusion, renal artery flow, renal oxygen consumption and T_2^* respectively
 - Peripheral blood oxygen saturation by pulse oximetry
 - Blood gas analysis

Then a standardized lunch will be given. Exactly six hours after intervention, test battery B will be repeated:

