- Test battery B (+6 hours)
 - MRI session with two measurements of: Renal perfusion, renal artery flow, renal oxygen consumption and T_2^* respectively
 - Peripheral blood oxygen saturation by pulse oximetry
 - Blood gas analysis

Finally, an optional dinner will be offered. See table 1 for a detailed timetable over visit 2.

Table 1

Time	Patients with type 1 diabetes	Healthy Controls
08:00	Kidney MRI (baseline)	Kidney MRI (baseline)
08:30	Blood oxygen saturation (baseline)	Blood oxygen saturation (baseline)
08:40	Arterial blood sample and analysis (baseline)	-
09:00	Intervention: 50 mg SGLT2i/placebo	-
09:00	Standardized morning meal	Standardized morning meal
12:00	Kidney MRI (+3 hours from intervention)	-
12:30	Blood oxygen saturation (+3 hours)	-
12:40	Arterial blood sample and analysis (+3 hours)	-
13:00	Standardized lunch	-
15:00	Kidney MRI (+6 hours from intervention)	-
15:30	Blood oxygen saturation (+6 hours)	-
15:40	Arterial blood sample and analysis (+6 hours)	-
16:00	Optional dinner	-

Timetable over visit 2

Visit 3 (day 28±6) at Steno Diabetes Center Copenhagen

The study participant will be instructed to take 50 mg dapagliflozin / placebo at the time 21:00 on the evening before visit 3. The study participant will come fasting from the morning and abstinent from medication, alcohol and tobacco use except long-acting insulin, 24 hours before the visit. The study participant is not allowed to do strenuous exercise 24 hours prior to the examination. Visit 3 will take approximately one hour. The following measures and samples are obtained:

- Test battery A (baseline)
 - Analysis of mitochondrial function of peripheral blood monocytes
 - Sample kept in research biobank for analysis of inflammatory markers
 - Baroreflex sensitivity assessed by continuous ECG and blood pressure

Visits 4 (day 42±6) and 5 (day 66±6)

Apart from study medication/placebo, study visits 4 and 5 will be identical to visits 2 and 3 but crossed over in terms of SGLT2i/placebo. Table 2 shows study timetable for randomized patients.

Table 2

Visit	Information visit	V1	V2	V3	V4	V5
Site	SDCC	SDCC	RHG	SDCC	RHG	SDCC
Week	0	1	2	4	6	8
Day	0	7	14	28	42	66
Tolerance (\pm days)		± 6				
General						
Informed consent	x					
Assessment of in- and exclusion criteria	x					
If patient: Randomization	x					
Demography		x				
Concomitant medication		x				
Medical history		x				
Weight and height		x				
BP and heart-rate		x				
Routine biochemistry		x				
Endpoints						

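### On its plain reading, the 24-hour pre-visit medication rule bars mealtime and correction insulin in type 1 diabetes, and leaves a pump user with no permitted insulin

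*Combined protocol and SAP*

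**What the plan says.** Under Study visits, the Visit 1, Visit 2 and Visit 3 paragraphs carry the same preparation rule: participants come "fasting from the morning and abstinent from medication, alcohol and tobacco use except long-acting insulin, 24 hours before the visit". The paragraph on the last two visits extends it: "Apart from study medication/placebo, study visits 4 and 5 will be identical to visits 2 and 3".

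The Visit 3 paragraph places a home dose immediately before the rule: "The study participant will be instructed to take 50 mg dapagliflozin / placebo at the time 21:00 on the evening before visit 3". Comparative treatment regimes gives the same schedule, "dapagliflozin 50 mg once on site for V2 and once at home on the evening before V3". Assessment of efficacy describes the measurements at these visits: "baroreflex sensitivity are obtained before intervention (baseline) and 12 hours after intervention".

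The two sequences under Randomization and blinding are "Dapagliflozin for V2 and V3 and placebo for V4 and V5" and "Placebo for V2 and V3 and dapagliflozin for V4 and V5".

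The diabetes criterion for entry is "Male or female patients >18 years of age with a diagnosis of type 1 diabetes (WHO criteria)". Neither the inclusion nor the exclusion criteria mention an insulin regimen or insulin pumps. The nearest exclusion concerns metal inside the body.

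**The concern.** The rule names insulin and exempts one kind of it, so a reader cannot simply assume that mealtime insulin was meant to be allowed. The fast begins only on the morning of the visit, so meals eaten the day before fall inside the 24 hours. No other section supplies a rule for mealtime, correction or pump insulin.

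What is at stake is patient safety. All randomized patients have type 1 diabetes, and the instruction, followed literally, withholds insulin they need. The protocol itself lists ketoacidosis, as a very rare event, among the effects of the drug. Its reassurance on the 50 mg dose cites a 12-week dose-ranging study (reference 20) whose title places it in type 2 diabetes, so that citation does not cover type 1 patients who are omitting mealtime insulin. The protocol also says that side effects were not seen after single doses and that dapagliflozin is approved in type 1 diabetes. Neither statement tells a patient which insulin to take the day before a visit.

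**Working it through.** The plan states no figure on this point. The check is a reading of the rule against the schedule, with simple counts of where it applies.

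**Step 1. Which insulin is permitted in the 24 hours (plain reading).**

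| Insulin | Status under the rule |
|---|---|
| Long-acting (basal) injection | Permitted, named exception |
| Mealtime dose on the previous day | Not permitted |
| Correction dose | Not permitted |
| Pump insulin | Not permitted, unless it counts as long-acting |

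The last row assumes that a pump does not deliver long-acting insulin. That is general clinical knowledge, not a statement in the protocol. The number of pump users is not given; the possible range is 0 to 15.

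**Step 2. How many patient-visits the rule governs.** Inputs: 15 patients with type 1 diabetes (Study population) and five visits (Table 2).

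- 15 patients × 5 visits = 75 patient-visits.

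**Step 3. How many of these windows contain an active home dose.** Each sequence gives dapagliflozin in one period only, so each patient takes one active home dose, before Visit 3 or Visit 5.

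- 15 × 1 = 15 patient-visits; 15 / 75 = 20%.
- Remainder: 15 at Visit 1, before any study drug; 15 × 2 = 30 at Visits 2 and 4; 15 on placebo at Visit 3 or Visit 5. Together 15 + 30 + 15 = 60, and 60 + 15 = 75.

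**Step 4. Timing at Visits 2 and 4.** Table 1 starts the day at 08:00 and gives the dose at 09:00. The pre-visit window runs from 08:00 the day before to 08:00 on the day, and ends before that on-site dose.

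**Step 5. Timing at Visits 3 and 5.** There is no clock timetable for these visits. Taking the 21:00 dose and the stated 12 hours, measurement falls at 21:00 + 12 h = 09:00. The window then runs from 09:00 to 09:00, and the drug overlaps its last 12 of 24 hours. The Background gives a half-life of about 17 hours, longer than those 12 hours.

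**Step 6. What the overlap contains.** From 21:00 to 09:00 is the night and the morning fast. Lunch and a dinner at a usual hour come before the dose. What remains inside the overlap is basal insulin for a pump user, correction doses for anyone, and high glucose carried over from a dinner eaten without insulin. Patients on long-acting insulin keep their basal cover.

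**Step 7. The other reading of the sentence.** The 24 hours could attach only to alcohol and tobacco, with medication withheld from the morning. The previous day's meals would then be covered by usual insulin. Even so, the exception would still name only long-acting insulin, leaving pump basal insulin and correction doses unaddressed that morning.

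**The case against.** The strongest reply is that the sentence was not drafted as an exhaustive rule. It strings together a fast, three abstentions, one exception and a time limit, and the time limit may not belong to all of them. Taken literally at Visit 3, it would forbid the study dose that the sentence before it instructs the patient to take. If intent rescues the study dose, intent might rescue mealtime insulin too. Patients also act on the written and oral information described under Recruitment and Participant information/informed consent, and the written text is not among the documents. A diabetes centre may well never have meant to stop mealtime insulin. The protocol has general safeguards as well: exclusion at the investigator's judgement, withdrawal for safety, and management of complications.

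Much of this stands. The milder reading is possible, and practice at the site is unknown. But the study dose has an explicit instruction that settles its case, and mealtime and pump insulin have none anywhere in the protocol. The general safeguards are not insulin rules. An insulin instruction in type 1 diabetes that can be read two ways, where the plainer reading is the unsafe one, is worth correcting whatever was intended.

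A reader might also infer that active drug coincides with missed mealtime doses in general. The timing does not support that: the overlap is mainly overnight, after the day's usual meals.

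**Conclusion.** The wording needs correction. On its plain reading, the rule bars mealtime and correction insulin for 24 hours before every visit while meals continue until the morning, and it leaves a pump user without long-acting insulin with nothing permitted. It governs 75 planned patient-visits. In 15 of them (20%), one per patient, it coincides for about 12 hours with an active 50 mg home dose; there the concern is limited to pump basal insulin, correction doses and carry-over from an uncovered dinner.

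This rests on three assumptions: that the 24 hours applies to medication as well as to alcohol and tobacco, that Visits 3 and 5 take place about 12 hours after the 21:00 dose, and that pump insulin is not long-acting.

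It would be tempting to read the counts as patients harmed, or to conclude that ketoacidosis is to be expected. The documents support neither. The counts show where the rule applies, no event rate can be derived, and the number of pump users may be zero. Nor should the rule be read as cancelling the home dose, since the intention to give it is clear. No endpoint, power or sample-size figure changes.

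**What to change.** At Visits 1, 2 and 3, replace the exception for long-acting insulin with: *except insulin (basal, mealtime, correction and pump)*. Add that only the meal-related dose is omitted while the patient is fasting on the morning of the visit, and that basal insulin, including pump basal, and correction doses continue. Visits 4 and 5 inherit the change. Correction doses should be named explicitly, because a general ban on bolus insulin during the fast would remove them on the morning after an active dose.

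Check that the written participant information, and what is said at the information meeting, match the new text.

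As a minor editorial point, add *and study medication* to the exception at Visit 3, and so at Visit 5, so that the rule no longer contradicts the 21:00 dose.

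The cost is a revised exception and one sentence at three places, a short phrase at Visit 3, and a check of the participant information. No visits, procedures or patients are added.
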